#### **11.4 Statistical Methods**

Descriptive analysis of data will be performed using the Student's *t*-test and Chi-square test. Association of numerical variables will be performed using Parson's correlation. For determination of whether the 2D or 3D monitor is correlated with intraoperative errors or other factors, binary logistic regressional models will be used.

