Statistical Methods	
Primary Statistical Hypothesis	N/A – This is a hypothesis generating pilot study. As a result no statistical hypothesis will be tested as part of this study.
Statistical Test Method	Outcomes will be assessed using descriptive statistics and comparative analysis.
Sample Size Parameters	
N/A – This is a hypothesis generating pilot study. As a result a sample size calculation is not required.
 
Fifty roux-en-y gastric bypass surgeries will be performed as part of this study; 25 consecutive surgeries will be performed using a 2D laparoscopic camera and 25 consecutive cases will be performed using a 3D laparoscopic camera.

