### **2.3 OR BlackBox® Platform**

The OR BlackBox® “Black Box” Platform is a multi-channel data recorder that records multiple synchronized feeds during a surgical procedure including:

- Panoramic views of the operating room
- View of the laparoscopic camera
- Intraoperative audio
- Room temperature

Video feeds of the room are sent to the Black Box from surveillance cameras that are affixed to the walls inside the OR, and audio feeds are captured using microphones placed at critical locations throughout the room. The Black Box subsequently integrates these recordings into a single interface to provide a comprehensive overview of the operation. The various video perspectives are displayed side-by-side with synchronized audio and a juxtaposed timeline that allows observers to flag any observable errors. This interface allows researchers to study the state of the entire OR for the period of time leading up to, during, and after a flagged error, which is critical for performing root-cause analyses of technical errors.

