### **5.2 Treatment Assignment**

A total of 50 laparoscopic roux-en-y gastric bypass surgeries will be assessed as part of this study. Twenty-five consecutive 2D laparoscopic surgeries and 25 consecutive 3D laparoscopic surgeries.

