## 9.2 Procedure (Hospital Visit)

- Laparoscopic 2D or 3D roux-en-y gastric bypass surgery
  - All study procedures will be video and audio recorded using 2 mounted cameras and auxilliary microphones. One camera will be focused on the surgical field and the second focusing on the OR door.
  - The laparoscopic video (internal subject view) will be recorded according to standard of practice.
  - All video and audio recordings will begin after the subject has been intubated and will end at skin closure prior to extubation.
- Procedure time (minutes) (skin-to-skin)
  - The Principal Investigator will perform the gastrojejunostomy (GJ) anastomosis
  - A surgical fellow will perform the jejunojejunostomy (JJ) anastomosis
- Adverse events (Including Clavien Classification of Surgical Complications (CCSC))
- Device deficiencies
- STAR Questionnaire will be completed by each surgical team member within 24 hours of surgical procedure

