**Table 1: Data Collection Schedule**

Procedure/Assessment	Screening/Baseline (Clinic Visit)	Procedure (Hospital Visit)	Post-Procedure OSATS and GERT	30 Day Follow-up  (Telephone Call)	Follow-up Visits
Visit Window	N/A	N/A	Within 30 Days After the Procedure	+/- 10 Days	Unscheduled Visit  (Clinic Visit)
Eligibility Criteria	X				N/A
Informed Consent Form	X				
Demographics	X				
Medical History	X				
Laparoscopic 2D or 3D Roux-en-Y Gastric Bypass Surgery		X			
STAR Questionnaire (Immediately following procedure in OR)		X 			
NASA Task Load Index		X			
Visualization and Physical Symptoms Questionnaire		X			
Surgical Team Demographic Questionnaire		X			
ESA: Video Feed Review (Completion of OSATS & GERT Tools)			X 		
Device Deficiencies			X		
Adverse Events		X	X		

 Immediately following the procedure, the STAR Questionnaire will be completed by each member of the OR team who participated in or attended the surgical procedure.

 Post-Procedure is not a subject follow-up visit, it is the point at which the video and audio feed of each surgical procedure will be reviewed by an ESA to complete the OSATS and GERT tools.

 Unscheduled Visits for subjects may be performed between protocol specified visits as deemed appropriate by the Investigator.

 End of study will be reached after completion of the 30 Day Follow-up Telephone Call, subject withdrawal, or lost to follow-up, whichever occurs first.

- Only the role of the surgical team member will be captured on this form, no names.
- NASA Task Load Index will be completed by each surgical team member within 24 hours of surgical procedure
- Visualization and Physical Symptoms Questionnaire will be completed by each surgical team member within 24 hours of surgical procedure
- Surgical Team Demographic Questionnaire

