## **11 Statistical Considerations**

### **11.1 Endpoints**

#### **11.1.1 Primary Endpoint**

There is no primary endpoint for this study as it is a hypothesis generating pilot study. This study will quantify operative performance and intraoperative errors after the introduction of the 2D and 3D technology using the following tools:

- Generic Error Rating Tool (GERT)
- Objective Structured Assessment of Technical Skill (OSATS)

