#### **11.2 Hypotheses**

N/A – This is a hypothesis generating pilot study. As a result no statistical hypothesis will be tested as part of this study.

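### Section 11.4 relates 2D/3D to intraoperative errors only by binary logistic regression, with no dependent variable or cut-point; if GERT yields a count per case, a count model would state the difference directly

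*Combined protocol and SAP*

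**What the plan says.** - Section 11.4 assigns the link between monitor type and errors to one regression model: "For determination of whether the 2D or 3D monitor is correlated with intraoperative errors or other factors, binary logistic regressional models will be used". It names no dependent variable, event, cut-point or effect measure.
- The same section lists Student's t-test and the chi-square test as descriptive analysis, and a correlation coefficient for numerical variables. None of these is tied to the error question.
- Section 11.1.1: "This study will quantify operative performance and intraoperative errors after the introduction of the 2D and 3D technology", using GERT and OSATS. How GERT is scored per case is not given.
- Section 2.3 says the recorder interface has "a juxtaposed timeline that allows observers to flag any observable errors". That fits a count per case but does not define one.
- The Synopsis (Statistical Test Method) adds only: "Outcomes will be assessed using descriptive statistics and comparative analysis".
- Section 11.2: "As a result no statistical hypothesis will be tested as part of this study".
- Section 9.2 records "Procedure time (minutes) (skin-to-skin)" for each case, but no section uses it as a denominator for errors.
- Section 5.2 fixes the groups: "Twenty-five consecutive 2D laparoscopic surgeries and 25 consecutive 3D laparoscopic surgeries".

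No count model and no exposure offset appears anywhere.

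**The concern.** Comparing 2D with 3D on performance and errors is the purpose of the study (Section 3). A binary logistic model needs a binary dependent variable, and the sentence in 11.4 allows two choices.

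- **Reading 1:** errors are reduced to yes/no and the monitor is the predictor.
- **Reading 2:** monitor type is the dependent variable and the error count is a predictor.

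If GERT gives a count, neither reading in general returns the ratio of error rates, which is the quantity that says how many fewer errors occur with one system. Section 5.3 says the data may generate a hypothesis for a larger study. An odds ratio whose size depends on an unwritten cut-point, or on case-to-case dispersion, is a poor basis for that.

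**Working it through.** The plan gives no effect size, error rate or power to reproduce.

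**Inputs.** From the plan (Sections 5.2 and 11.3): 25 cases per arm. Assumed: true rate ratio RR = 0.70 (3D/2D); 2D mean μ of 1 to 20 errors per case; variance μ + kμ², with k from 0 (Poisson) to 1. For scale, μ = 10 and k = 0.25 give a variance of 10 + 0.25 × 100 = 35.

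**Reading 1, effect of the cut.** OR = odds(Y ≥ c in 3D) / odds(Y ≥ c in 2D), from exact negative binomial tails with means 7 and 10, k = 0.25:
- c = 5: probabilities 0.677 and 0.831; OR = 2.093/4.918 = 0.43
- c = 10: 0.245 and 0.466; OR = 0.324/0.873 = 0.37
- c = 15: 0.063 and 0.199; OR = 0.067/0.248 = 0.27

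**Reading 1, any-error cut.** With p0 = (1 + km)^(−1/k), or exp(−m) at k = 0, where m is the arm mean, the probability that the odds ratio has no finite, non-zero estimate is 1 − ∏ over arms of [1 − (1 − p0)^25 − p0^25].
- μ = 5, k = 0.25: p0 = 2.25^(−4) = 0.039 and 1.875^(−4) = 0.081; arm terms 0.630 and 0.879; 1 − 0.630 × 0.879 = 45%
- μ = 10, k = 0.25: p0 = 0.0067 and 0.0175; arm terms 0.154 and 0.357; 1 − 0.154 × 0.357 = 95%
- Over k from 1 to 0: 1% to 92% at μ = 5, and 12% to 100% at μ = 10. At μ of 1 to 2 with k = 0.25 it is about 0%.

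**Reading 2.** The log ratio of two negative binomial densities with common k is linear in the count, so the odds ratio per extra error is RR × (1/k + μ) / (1/k + RR × μ). At k = 0 it is RR.
- k = 0: 0.70
- μ = 5, k = 0.25: 0.70 × 9/7.5 = 0.84
- μ = 10, k = 0.25: 0.70 × 14/11 = 0.89
- μ = 20, k = 1: 0.70 × 21/15 = 0.98
- Poisson errors with a gamma-distributed operating time of CV 25% (k = 0.25² = 0.0625), μ = 10: 0.70 × 26/23 = 0.79

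**Special cases.** Reading 2 equals the rate ratio for Poisson counts with equal exposure. The any-error cut equals it at k = 1, where the odds of any error equal μ, giving 7/10 = 0.70 at μ = 10. The plan cannot know in advance that either holds.

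**Power (simulated, two-sided 5%, k = 0.25, μ = 1/2/5/10/20).**
- Quasi-Poisson count model: 16/26/42/52/60%
- t-test on counts: 17/26/42/52/59%
- Median split, chi-square or likelihood-ratio test: 15/22/34/41/47%
- Monitor as outcome, likelihood-ratio test: 18/28/44/52/62%

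The first three rows use 20,000 runs per cell and the last 3,000. The median-split loss at μ = 5/10/20 is 42.2 − 33.5 = 8.7, 52.1 − 41.2 = 10.9 and 59.7 − 47.2 = 12.5 points. The split rejects 6.6% to 7.1% under the null at those means, against 4.9% for the count model, so its loss is not due to strictness. Reading 2 rejects about 5.6% under the null at μ = 10; its slightly higher power should be read as no loss, not as a gain.

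**What a count model would report.** Typical 95% CI around 0.70 at μ = 5/10/20, k = 0.25, with factors 1.49/1.41/1.37: 0.47–1.04, 0.50–0.99, 0.51–0.96.

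**The case against.** The strongest reply has four parts.

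- **No stated target is missed.** The plan never names a rate ratio. Section 11.4 asks about association, and logistic regression in either direction addresses association. This stands: the plan does not contradict itself here, and no figure in it is wrong.
- **Reading 2 is plausible and efficient.** The monitor is the one variable in that sentence that is certainly binary, and this reading needs no cut-point and loses no power. This also stands. A reader might infer that the logistic model wastes information whichever way it is read; the power figures do not support that. The power loss and the non-estimable odds ratio belong to Reading 1 alone. Reading 2's odds ratio is a valid parameter on a per-error scale; it just does not give the size of the rate difference.
- **The t-test covers it.** A reader might infer that the plan has no sound way to compare error counts. That goes too far: the listed t-test compares mean counts with about the power of a count model, and per-arm means, if reported, would let the ratio be worked out by hand. But 11.4 neither assigns the t-test to this question nor commits to reporting a ratio with an interval.
- **GERT may not be a count.** The documents do not define its output, so the argument for a count model is conditional. The need to name the dependent variable is not.

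It is also true that the arms are consecutive series, so a rate ratio would not isolate the effect of 3D.

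**Conclusion.** The point holds as one of under-specification and fit. Section 11.4 gives a binary model for errors without a binary outcome. If GERT yields a count, one true 30% reduction could appear as an odds ratio of 0.27 to 0.43 under Reading 1 (the three cuts at μ = 10, k = 0.25) or 0.84 to 0.98 under Reading 2 (the three negative binomial cases), depending on choices and dispersion that the plan leaves open. No test is planned, so error rates of a test are not at stake; the damage is to estimation and to what a later study can take from the result. The size rests wholly on assumed means, dispersions and a rate ratio of 0.70. The non-estimability range in particular is too wide to predict what this study would see. The change is worth making because it is cheap, not because the plan would otherwise be unable to compare the arms.

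**What to change.** In Section 11.4:

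1. State the per-case GERT variable and the dependent variable of each model.
2. Where the variable is a count, replace binary logistic regression with quasi-Poisson or negative binomial regression of the count on arm. Report the rate ratio, its 95% CI and the dispersion, labelled as an exploratory, non-randomised comparison.
3. Add log skin-to-skin time as an offset in a sensitivity analysis only, because operating time may itself differ between arms.
4. Keep logistic regression for truly binary outcomes, with the event defined in advance.

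The cost is a change of wording before analysis. GERT review and procedure time are already collected, so no patients or data are added. The statistician must confirm that the chosen model is available in the software named in Section 11.5.

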## 1 Introduction

Data published in 2008 estimated the global number of surgical procedures performed annually as 234 million with a rate of major perioperative complications reported between 3% and 17% in industrialized countries. As a derivative of these figures, it is estimated that approximately 7 to 40 million major complications occur worldwide each year. Studies have shown that between 39.6% and 54.2% of surgical complications occur in the operating room (OR); furthermore, it has been suggested that one third to half of all surgical errors are potentially avoidable. These findings have brought considerable attention to quality improvement in the technically demanding field of laparoscopic surgery wherein the risk of intraoperative error is increased by the sociotechnical complexity of the operative environment. In particular, there has been growing interest in evaluating surgical processes from a human factors point of view, as human factors, such as fatigue and mental workload, have become increasingly recognized as root causes of adverse surgical events and outcomes.

Among the most commonly reported errors in conventional laparoscopic surgery are technical errors associated with impaired depth perception; laparoscopic surgeons rely on two-dimensional (2D) video displays to guide their work in a three-dimensional (3D) space, resulting in the loss of depth perception and spatial orientation, as well as the experience of increased visual and cognitive load. Technical errors can be defined as manual errors of the surgeon (e.g. damage to adjacent structures) and procedural errors due to a lack of surgeon proficiency or experience. These errors are frequently described, especially when evaluating closed malpractice cases. These factors have been extensively examined but still remain controversial. A major limitation of error analyses of closed malpractice cases and root cause analyses of complications is the hindsight bias introduced through the knowledge of patient outcome.

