### **5.1 Scale and Duration**

A total of 50 subjects, 25 undergoing 2D laparoscopic surgery and 25 undergoing 3D laparoscopic surgery, will be enrolled and treated at 1 study site in Canada. Each subject will be followed for approximately 30 days following the study procedure. It is anticipated for the entire study to last 9 months.

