#### **11.1.2 Secondary Endpoints**

1. Clinically significant adverse events related to the device(s) and/or procedure.
  - Clinically significant is defined as any deviation from the normal surgical or post operative course that requires special treatment or action.

2. Operating room (OR) team's perception of human factors and teamwork following each procedure using the Modified Surgical Team Assessment Record (STAR) questionnaire.
3. NASA Task Load Index to assess mental workload and frustration
4. Visualization and Physical Symptoms Questionnaire
5. Surgical Team Demographic Questionnaire

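### With 25 per arm, the ordinary logistic odds ratio for a rare binary outcome often has no finite value, and Section 11.4 plans no interval or alternative

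*Combined protocol and SAP*

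**What the plan says.** Section 11.4 is the only text on statistical methods beyond the synopsis, which promises descriptive and comparative analysis in general terms. For categorical data 11.4 names the "Chi-square test". To relate the monitor type to intraoperative errors "or other factors, binary logistic regressional models will be used". It does not mention confidence intervals, exact or penalised methods, covariates, or what to do when counts are small. Section 11.5 fixes the software as SPSS 22.0.

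Section 5.1 sets the size: "A total of 50 subjects, 25 undergoing 2D laparoscopic surgery and 25 undergoing 3D laparoscopic surgery, will be enrolled". The clearest binary outcome is the first secondary endpoint in 11.1.2, "Clinically significant adverse events related to the device(s) and/or procedure", where clinical significance means "any deviation from the normal surgical or post operative course that requires special treatment or action". It has no analysis method of its own, and no event rate is assumed for it. The only complication rate in the documents is background in the Introduction: a "rate of major perioperative complications reported between 3% and 17% in industrialized countries".

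Sections 11.2 and 11.3 state that no hypothesis is tested and that no sample size calculation is needed. Section 5.3 says the data may be used to generate a hypothesis for a larger, pivotal study.

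**The concern.** With 25 operations per arm, an uncommon outcome can easily be absent from one arm or from both. Ordinary maximum likelihood then has no finite, non-zero odds ratio to report. Software typically prints a huge coefficient with a meaningless standard error, or a convergence warning. The usual condition for the chi-square approximation, expected counts of at least 5, also tends to fail.

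Because this is a pilot without hypotheses, its useful product is a set of estimates for planning the next study. An infinite or missing odds ratio cannot serve that purpose, and 11.4 offers nothing to put in its place.

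**Working it through.** There is no power, alpha or sample size figure in the plan to reproduce.

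**Inputs.** n = 25 per arm (5.1). Event rate p: 3% to 17% as an illustration (Introduction; major complications across surgery), plus an assumed 25% because the endpoint is broader. Two-sided 0.05 is assumed for the chi-square check, since the plan gives no alpha.

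**Step 1: expected events.** 25 × 0.03 = 0.75 and 25 × 0.17 = 4.25 per arm, so 1.5 to 8.5 in total.

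**Step 2: no finite odds ratio.** An arm has no events with probability q = (1 − p)^25. With equal rates, at least one arm is empty with probability 1 − (1 − q)². The chance that an arm consists only of events is negligible at these rates.

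- 3%: q = 0.467; 1 − 0.533² = 0.716
- 5%: q = 0.277; 1 − 0.723² = 0.478
- 10%: q = 0.0718; 1 − 0.9282² = 0.138
- 17%: q = 0.0095; 1 − 0.9905² = 0.019
- 25% (assumed): q = 0.00075; 1 − 0.99925² = 0.0015, about 0.2%

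If one arm has half the rate of the other, the probability is 1 − (1 − q₁)(1 − q₂). For 10% vs 5% this is 1 − 0.928 × 0.723 = 0.329. The same formula gives 83% for 3% vs 1.5%, 66% for 5% vs 2.5%, and 12% for 17% vs 8.5%.

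**Step 3: chi-square over all tables.** All 26 × 26 outcomes were enumerated with equal rates. With equal arms, an expected event count below 5 means nine or fewer events in total.

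| Rate | Expected count below 5 | Chi-square (uncorrected) type I error |
|---|---|---|
| 3% | 100% | 0.6% |
| 5% | 100% | 2.0% |
| 10% | 97.5% | 4.9% |
| 17% | 66.0% | 5.5% |

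The rule of thumb fails in most trials, but the error rate stays near or below 5%. Fisher's test over the same range has size 0.01% to 2.1%, which is much more conservative.

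**Step 4: one sparse table, 4/25 vs 0/25.** With the arms as the fixed margins, the p-values are chi-square 0.037, Barnard 0.041, Boschloo 0.065 and Fisher 0.110. The answer depends on the test chosen.

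**Step 5: what the alternatives give for that table.**

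- *Ordinary logistic regression:* infinite odds ratio.
- *Firth-penalised:* for a single binary factor this amounts to adding 0.5 to each cell. Odds ratio = (4.5 × 25.5)/(21.5 × 0.5) = 10.7. Standard error of the log = √(1/4.5 + 1/21.5 + 1/0.5 + 1/25.5) = 1.52. Wald 95% interval 0.54 to 210.
- *Risk difference:* 0.16 − 0 = 0.16. The Wilson score limits are 0.064 to 0.347 for 4/25 and 0 to 0.133 for 0/25. Combined by Newcombe's method, the lower limit is 0.16 − √(0.096² + 0.133²) = −0.004 and the upper is 0.16 + √(0.187² + 0²) = 0.347. The result is finite and readable.

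**The case against.** The strongest objection is that the plan may never meet the problem. The logistic sentence names intraoperative errors, and adverse events come in only through its reference to other factors. The documents give no error rate and no rule for making errors binary. The 3-17% figure describes major complications across all surgery, whereas the endpoint covers any departure from the normal course needing action, so its rate may well be higher. At an assumed 25% the odds ratio fails in about 0.2% of trials. All of this stands, and it makes the concern conditional on a low rate. The converse holds too: if errors are made binary and nearly every case has one (95% assumed), the odds ratio fails at the other end in 48% of trials.

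A reader might also infer that chi-square would produce false positives, or that exact tests would overturn a 4 vs 0 result. The documents and the arithmetic do not support either. Average error control is acceptable, Barnard's exact p for 4 vs 0 is 0.041, and a 4-0 split in either direction occurs in at most about 2.2% of trials with equal rates. The plan sets no significance level and tests no hypothesis, so nothing would formally be declared significant.

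Finally, the Firth interval of 0.54 to 210 carries little information. That is true. It at least shows the uncertainty, and the risk difference is the better main summary.

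**Conclusion.** The point holds in a conditional form and is minor. If a binary outcome is rare, the model in 11.4 often cannot supply a finite 2D-versus-3D odds ratio: in 72% of trials at 3% and 48% at 5%, occasionally at 10% (14%, or 33% if one arm has half the rate), and rarely at 17% (2%, or 12%). These figures assume independent operations. The 3-17% range is an illustration; it should not be read as the protocol's expected rate for this endpoint, because none is stated.

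The chi-square test is not the main problem. Its p-value in a single sparse table depends on the choice of test, which is a reason to lead with intervals. The consequence is a missing or unusable estimate for planning the pivotal study; a false confirmatory claim is not at issue.

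**What to change.** In 11.4, state that for clinically significant adverse events, and for any other sparse binary outcome, the main summary is the count in each arm and the risk difference with a score-based or exact 95% confidence interval. Add that if a logistic model is fitted and either arm has no events, or only events, Firth-penalised estimation replaces ordinary maximum likelihood.

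The cost is a sentence or two of SAP text. The intervals will be wide, as they should be with this much information. Whether SPSS 22.0, named in 11.5, provides these methods should be checked before analysis; a second package may have to be added there. No change to sample size or data collection is needed.
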